### **5.5.2** Replacement Subjects

Approximately 72 healthy subjects are planned for enrollment, of which 24 subjects will be enrolled and randomized in Part 1 and 48 subjects will be enrolled and randomized in Part 2. Up to 18 subjects may be qualified as replacements. Thus, a maximum of 90 subjects may be exposed to study drugs and procedures during the study.

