### Across all study days (Primary Endpoint)

• Maximum concentration (observed peak drug concentration) (Cmax)

#### Days 1

- Maximum concentration (observed peak drug concentration) (Cmax)
- Time at which  $C_{max}$  occurs  $(T_{max})$

• AUC from time 0 to the sampling time corresponding to the last quantifiable concentration (Clast) (AUC0-t), calculated by the mixed linear logarithmic trapezoidal method

### Days 2 and 3

- Residual drug concentration (predose level) (Ctrough)
- 3 h post dose concentration

### Day 4

- Elimination rate constant (Kel), obtained by linear regression of the log-linear terminal phase of the concentration-time profile using at least 3 data points, excluding Cmax, otherwise Kel will not be determined. The acceptability criteria for determination of Kel will be a coefficient of regression more than or equal to 0.98.
   When Kel will not be determined, AUC0-inf and t1/2 will not be reported.
- Terminal half-life  $(t_{1/2})$ , calculated using the equation  $\ln 2/k$  after the last study drug application (on Day 4)
- Accumulation ratios, calculated using the following formula:

$$R_1 = AUC_{0-23} Day 4 / AUC_{0-23} Day 1$$

• AUC from time 0 extrapolated to infinity (AUC0-inf), calculated by the mixed linear-logarithmic trapezoidal method as:

$$AUC_{0\text{-inf}} = AUC_{0\text{-t}} + C_{last} / K_{el}$$

When the extrapolation represents more than 20%,  $AUC_{0-inf}$  and  $t_{1/2}$  will not be reported.

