Replacement subjects (if needed) will be assigned to the treatment group of the subject they are replacing.

The treatment groups are presented in Table 5-2.

**Table 5-2** Treatment Groups

Study Part	Subjects (n)	Treatment Group	Treatment
1	6	A	La Roche Posay (Cream), Anthelios SX Daily Moisturizer Cream, Face Sunscreen SPF 15 with Mexoryl SX
1	6	В	Hawaiian Tropic (Lotion); Island Sport Ultra- Light High Performance Sunscreen, SPF 50
1	6	С	Neutrogena (Spray) Ultra Sheer Body Mist SPF 45
1	6	D	Banana Boat (Spray); Sport Performance Coolzone Continuous Spray Sunscreen, SPF 50
2	12	Е	Hawaiian Tropic (Lotion); Island Sport Ultra- Light High Performance Sunscreen, SPF 50
2	12	F	Neutrogena (Aerosol Spray), Ultra Sheer Body Mist SPF 100
2	12	G	Supergoop (Non-Aerosol Spray), Sunscreen Mist with Vitamin C SPF 50
2	12	Н	Supergoop (Pump Spray), Sun Defying Sunscreen Oil with Meadowfoam SPF 50

All randomization information will be secured and housed in a locked storage area, accessible only by the randomization personnel and the assigned pharmacist and his or her verifier.

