# 5.9.2 Analysis Populations

The PK population will include all subjects who receive study drug and have at least 1 estimable PK parameter after dosing.

The safety population will include all subjects who receive at least 1 dose of any of the study drugs.

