1.2 Primary Objective (Part 2)

Part 2 is an open-label, 4-arm study in 48 healthy adult subjects with the following primary objective:

- To assess, where applicable, the pharmacokinetics and systemic absorption of the active components (avobenzone, oxybenzone, octocrylene, ecamsule, homosalate, octisalate and octinoxate, of 4 sunscreen products (1 sunscreen product in each arm) under maximal-use conditions.

Part 2 will include the sunscreen product with maximal avobenzone exposure from Part 1 and 3 additional new sunscreen formulations. More detailed information about the study (inclusion/exclusion criteria and schedule of events) can be found in the study protocol.

2 Sample Size

Approximately 72 healthy subjects are planned for enrollment, of which 24 will be assigned to Part 1 (randomized to 4 arms of 6 participants each) and 48 will be assigned to Part 2 (randomized to 4 arms of 12 participants each). Subjects are considered enrolled after determination by the Principal Investigator on Day 0 that they meet all eligibility criteria and are subsequently assigned a randomization/study identification number. The sample size was determined empirically and is typical for exploratory investigations of this type.

3 Analysis Populations

The analysis population will include all subjects who receive at least 1 dose of any of the study drugs and have PK sample data for the treatment period collected before dosing and at 1 or more time points after dosing.

The safety population will include all subjects who receive at least 1 dose of any of the study drugs.

4 General Statistical Considerations, Subject Disposition and Demographics and Baseline Characteristics

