All data will be presented in data listings. Data from subjects excluded from an analysis population will be presented in the data listings but not included in the calculation of summary statistics. The number of subjects who enroll in the study and the number and percentage of subjects who complete each assessment will be presented. The frequency and percentage of subjects who withdraw or discontinue from the study and the reason for withdrawal or discontinuation will be summarized. Continuous demographic and baseline characteristic variables (age, height, weight, body mass index) will be summarized overall and by treatment using descriptive statistics (number of subjects, mean, standard deviation [SD], median, interquartile range [IQR], and minimum and maximum). The number and percentage of subjects in each class of categorical demographic and baseline characteristic variables will also be summarized.

5 Pharmacokinetic (PK) Analyses and Primary/Secondary Outcomes

The PK sampling schedule for this study is summarized in Appendix A. The following PK parameters will be determined for each subject in Part 1 and Part 2:

Across all study days

- Maximum concentration (observed peak drug concentration) (C_{\max})

Day 1

- Maximum concentration (observed peak drug concentration) (C_{\max})
- Time at which C_{\max} occurs (T_{\max})
- AUC from time 0 to the 23 hour time point (C_{last}) (AUC_{0-23})

Days 2 and 3

- Residual drug concentration (predose level) (C_{trough})
- Concentration 3 hours after the last dose of the day

Day 4

- Maximum concentration (observed peak drug concentration) (C_{\max})
- Time at which C_{\max} occurs (T_{\max})
- Elimination rate constant (K_{el}) and terminal half-life ($t_{1/2}$); calculated after final dose using all the available data up to last study sample (144 hours for Part 1; 432 hours for Part 2)
- AUC from time 71 to the 95 hour time point (AUC_{73-95})
- AUC from time 0 extrapolated to infinity ($AUC_{0-\text{inf}}$) and/or last observed time point

Day 5, 6, 7, 10 (Part 2 only), 14 (Part 2 only) and 21 (Part 2 only)

- Residual drug concentration (C_{trough})

The primary and secondary outcomes of this study are as follows:

Primary Outcome:

1. Maximum* Avobenzone concentration (C_{\max})

Secondary Outcomes:

1. Maximum* Oxybenzone concentration (C_{\max})
2. Maximum* Octocrylene concentration (C_{\max})
3. Maximum* Ecamsule concentration (C_{\max})
4. Maximum* Homosalate concentration (C_{\max})

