5. Maximum* Octisalate concentration (C_{\max})

6. Maximum* Octinoxate concentration (C_{\max}) (Part 2 Only)

* observed maximum;

Note that C_{\max} could occur on any of the days of the study. PK parameters C_{\max} , C_{last} , C_{trough} , T_{\max} , AUC_{0-t} , K_{el} , $t_{1/2}$ and $AUC_{0-\text{inf}}$, will be summarized using descriptive statistics (number of subjects, mean, standard deviation [SD], coefficient of variation [CV], median, minimum, and maximum) for the days above for avobenzone, oxybenzone, octocrylene, ecamsule, homosalate, octisalate and/or octinoxate (depending on whether the specific sunscreen formulation contains each of the active ingredients; see Attachment B) in Part 1 and 2. The PK parameters will be analyzed using non-compartmental methods based on actual sampling times. Mean and individual concentration-time profiles will be presented in graphs.

6 Safety Analyses

All AEs will be coded using the latest version of the Medical Dictionary for Regulatory Activities (MedDRA). The incidence of treatment-emergent adverse events (TEAEs), organized by system organ class and frequency, will be summarized by seriousness, severity, relationship to treatment, and by treatment at onset of the TEAE. A detailed listing of serious AEs and TEAEs leading to withdrawal will also be provided.

Clinical laboratory results (hematology, serum chemistry, and urinalysis) will be summarized using descriptive statistics (number of subjects, mean, SD, minimum, median, and maximum). Clinical laboratory results will be classified as normal or abnormal, according to the reference ranges of the individual parameter. The number and percentage of subjects with abnormal laboratory results will be provided. No statistical testing will be performed on clinical laboratory data.

Vital sign measurements (blood pressure, heart rate, respiratory rate, and oral body temperature), safety 12-lead ECG results, and changes from Baseline for these parameters will be summarized by treatment and time point using descriptive statistics (number of subjects, mean, SD, minimum, median, and maximum). Physical examination findings will be presented in a data listing, and abnormal physical examination findings will be recorded as AEs.

All concomitant medication usage and medications that changed in daily dose, frequency, or both since the subject provided informed consent will be summarized for each subject.

7 Missing Data

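### The PK population sets no minimum exposure, so any subject who stops during Days 1-4 stays in the primary Cmax summary and can pull it below maximal-use exposure

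*SAP*

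**What the plan says.** **Who is summarised.** SAP section 3: "The analysis population will include all subjects who receive at least 1 dose of any of the study drugs and have PK sample data". The sentence goes on to require that subjects "have PK sample data for the treatment period collected before dosing and at 1 or more time points after dosing". Protocol 5.9.2: "The PK population will include all subjects who receive study drug and have at least 1 estimable PK parameter after dosing". Under SAP section 4, only data from subjects outside the population are left out of summary statistics.

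**What is summarised.** The SAP section 5 primary outcome is "Maximum* Avobenzone concentration", the observed maximum, which "could occur on any of the days of the study". Protocol 5.7.1.4 likewise labels Cmax across all study days as the primary endpoint. SAP section 5 also lists Cmax separately for Day 1 and Day 4. The statistics are n, mean, SD, CV, median, minimum and maximum.

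**Target exposure.** The objective in both parts is absorption under maximal-use conditions. Protocol 5.8.1 plans four applications a day for four days in Part 1, and one on Day 1 then four a day on Days 2-4 in Part 2.

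**Replacement.** Protocol 5.5.2: "Up to 18 subjects may be qualified as replacements. Thus, a maximum of 90 subjects may be exposed to study drugs". Protocol 5.8.2.1: "Replacement subjects (if needed) will be assigned to the treatment group of the subject they are replacing". Neither says when a subject is replaced, or whether the replaced subject's data stay in the arm summary.

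**The concern.** A subject who leaves on Day 1 contributes a Cmax labelled as spanning all study days but drawn from one day of dosing. For any one subject, a maximum over fewer applications and samples cannot exceed the maximum over the full course. Pooling such a value with full-course values therefore tends to lower the arm summary. A maximal-use study is meant to avoid understating exposure, so this is the unwelcome direction.

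The gap exists under either population definition, so reconciling the SAP and protocol definitions would not close it. It matters most in Part 1, where arms hold only six subjects and avobenzone exposure also decides which product goes forward to Part 2.

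**Working it through.** **1. The plan's own figures.** Planned enrolment is 4 x 6 + 4 x 12 = 72. With up to 18 replacements, 72 + 18 = 90, which agrees with protocol 5.5.2. Planned applications are 4 x 4 = 16 in Part 1 and 1 + 3 x 4 = 13 in Part 2.

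**2. How little is needed for entry.** SAP Attachment A has samples at 0 h and 0.5 h. One application and those two draws meet the SAP sampling condition. Under the protocol rule, an observed Cmax is estimable from one quantifiable post-dose sample.

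**3. Formula.** Let r be an early stopper's Cmax divided by the full-course Cmax, n the number of full-course subjects, and k the number of stoppers kept. As a share of the full-course mean, the arm mean is:
- stoppers kept and replaced: (n + k r)/(n + k)
- stoppers kept, not replaced: (n - k + k r)/n

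**4. Effect of replacement alone** (k = 1, r = 0.25 assumed).
- Planned arm of 12: (11 + 0.25)/12 = 93.8% without replacement; (12 + 0.25)/13 = 94.2% with it.
- Planned arm of 6: (5 + 0.25)/6 = 87.5% without; (6 + 0.25)/7 = 89.3% with it.

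Replacement makes the dilution slightly smaller. The cause is keeping the early stopper.

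**5. Plausible r.** The documents give no half-life, so this step rests on assumptions: linear one-compartment superposition of equal applications, elimination half-life 12-72 h, absorption half-life 2-10 h, read at the planned sampling times. A leaver is taken to give the next morning's pre-dose sample (23, 47 or 71 h). Leaving before it could make r lower still.

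| Leaves after | r | Arm mean, one leaver kept and replaced | Fall in mean |
|---|---|---|---|
| Part 2 Day 1 | 0.08-0.19 | 12.08/13 to 12.19/13 = 92.9-93.8% | about 6-7% |
| Part 2 Day 2 | 0.40-0.76 | 12.40/13 to 12.76/13 = 95.4-98.2% | about 2-5% |
| Part 2 Day 3 | 0.73-0.95 | 12.73/13 to 12.95/13 = 97.9-99.6% | about 0.4-2% |
| Part 1 Day 1 | 0.27-0.71 | 6.27/7 to 6.71/7 = 89.6-95.9% | about 4-10% |

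**6. Other statistics.** A log-normal simulation (assumed CV 50-80%, one stopper added, r from 0.1 to 0.5) compared each statistic with its full-course value:
- median: about 86-92% (n = 6) and 93-96% (n = 12)
- minimum: about 19-87%
- maximum: ratio 1.00-1.01

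**7. Day 4 Cmax.** A Day 1 leaver has no Day 4 samples and cannot enter this summary.

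**The case against.** **The effect is conditional.** No dropout rate is given. Subjects live in the unit from Day 0 to Day 7, every application is given or observed by clinic staff, and inclusion criterion 9 selects people judged highly likely to complete. With no early stopper the bias is zero. This stands, and the point is stated conditionally.

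**Eighteen replacements is a ceiling.** A reader might infer that the sponsor expects 18 early stoppers, or that adding replacements causes the dilution. The text supports neither. Replacements apply only if needed, they are not restricted to people who stop during dosing, and step 4 shows that they lessen the effect. A Part 2 subject lost at the Day 10, 14 or 21 visit has already had all 13 applications and dilutes nothing.

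**Large effects need a worst case.** One can reach an 18% fall in a Part 2 arm: (12 + 3 x 0.10)/15 = 82%. That needs three Day 1 leavers in one arm and an assumed r of 0.10. Nothing in the documents makes this likely.

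**The plan already reveals much of this.** The separate Day 4 Cmax, reported n, full listings, discontinuation reasons and individual profiles let a careful reader find a one-day subject. They limit the harm but leave the headline mean, median and minimum uncorrected.

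**A completers-only set has its own bias.** It selects on a post-randomisation event, and withdrawal for an adverse event may be related to absorption. This is a good argument against replacing the all-dosed summary. It is no argument against showing both.

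**Conclusion.** The point holds in conditional form. As written, both population rules keep a subject with as little as one application in the primary Cmax summary, and nothing says how a replaced subject's data are used. If anyone stops during Days 1-4, the arm mean, median and minimum can understate exposure under maximal use.

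One early stopper would probably shift the arm mean by a few percent, and by about 10% at most for a Day 1 leaver in a Part 1 arm. These sizes rest on the assumed one-compartment model and half-lives; the true size cannot be derived from the documents. A reader might infer that all reported exposure is diluted. That goes too far: it depends on early stopping, and the arm maximum and the Day 4 Cmax are essentially untouched by Day 1 leavers.

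This should be settled in the SAP before the data are summarised. The study is open-label, and a choice made later could be influenced by the concentrations seen.

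**What to change.** In SAP sections 3 and 5:

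1. Pre-specify that the across-all-days Cmax is summarised for subjects who received every planned application through the last one on Day 4 (16 in Part 1, 13 in Part 2).
2. Present the same summary for all dosed subjects in the SAP section 3 population beside it.
3. List partly dosed and replaced subjects with the number of applications each received, and state that a replaced subject's data remain in the all-dosed summary.
4. Apply the same rule to the Part 1 avobenzone comparison that selects the Part 2 product. The protocol's treatment list already names the lotion carried forward, so if that choice has been made, use the rule to check it.

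**Cost.** SAP wording, one extra table and one listing, from application records that protocol 5.8.6 already requires in the eCRF. Dosing, sampling and enrolment do not change. The full-course set may have a smaller n and is selected after randomisation, which is why both summaries are needed. If nobody stops early or misses an application, they coincide.

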Attachment A. Pharmacokinetic Sample Collection Schedule

Pharmacokinetic blood samples (approximately 10 mL per sample) will be collected for determination of avobenzone, oxybenzone, octocrylene, ecamsule, homosalate, octisalate and octinoxate plasma concentrations (where applicable to the different sunscreen formulations), at the following time points (the time limit for PK sample draws can be +/- 5 minutes from the nominal time):

- Day 1: 0 and 0.5, 1, 1.5, 2, 3 (Part 2 only), 4, 6, 8, 9, 10, 12, and 14 hours after initial dose
- Day 2: 23, 28, 33 h
- Day 3: 47, 52, 57 h
- Day 4: 71, 73, 74, 76, 78, 81, 82, 84 and 86 h
- Day 5: 95 hours
- Day 6: 120 hours
- Day 7: 144 hours
- Day 10: 216 hours (Part 2 only)
- Day 14: 312 hours (Part 2 only)
- Day 21: 480 hours (Part 2 only)

NOTE: when a time point corresponds with sunscreen administration, the PK sample will be collected before sunscreen administration.

Attachment B. Randomization Schedule

Randomization in this study is unblinded.

After screening, subjects will be randomized to one of 4 treatment sequences in either Part 1 (24 subjects) or Part 2 (48 subjects). Example of treatment codes from the study protocol:

- Treatment sequences of Part 1:
 - A: La Roche Posay (Cream), Anthelios SX Daily Moisturizing Cream with Sunscreen, SPF 15 with Mexoryl SX (6 subjects): Avobenzone (2%), Ecamsule (2%) and Octocrylene (10%)
 - B: Hawaiian Tropic (Lotion); Island Sport Ultra-Light High Performance Sunscreen, SPF 50 (6 subjects): Avobenzone (3%), Oxybenzone (4%) and Octocrylene (6%)
 - C: Neutrogena (Spray), Ultra Sheer Body Mist SPF 45 (6 subjects): Avobenzone (3%), Oxybenzone (6%), Octocrylene (2.35%), Homosalate (15%) and Octisalate (5%)
 - D: Banana Boat (Spray); Sport Performance Coolzone Continuous Spray Sunscreen, SPF 50 (6 subjects): Avobenzone (3%), Oxybenzone (5%) and Octocrylene (10%)

- Treatment sequences of Part 2:
 - E: Hawaiian Tropic (Lotion); Island Sport Ultra-Light High Performance Sunscreen, SPF 50 (12 subjects): Avobenzone (3%), Oxybenzone (4%) and Octocrylene (6%)
 - F: Neutrogena (Aerosol Spray), Ultra Sheer Body Mist SPF 100 (12 subjects): Avobenzone (3%), Oxybenzone (6%), Octocrylene (10%), Homosalate (15%) and Octisalate (5%)
 - G: Supergoop (Non-Aerosol Spray), Sunscreen Mist with Vitamin C SPF 50 (12 subjects): Avobenzone (3%), Octocrylene (10%), Homosalate (10%), Octisalate (5%) and Octinoxate (7.5%)
 - H: Supergoop (Pump Spray), Sun Defying Sunscreen Oil with Meadowfoam SPF 50 (12 subjects): Avobenzone (3%), Homosalate (10%), Octisalate (5%) and Octinoxate (7.5%)

The script performs randomization across treatment groups; all subjects in Part 1 will be studied in 1 cohort (cohort 1) and subjects in part 2 will be studied in 2 cohorts (cohorts 2 and 3).

Treatment schedule

RANDID	PART	COHORT	SEQ
1001	1	1	D
1002	1	1	A
1003	1	1	C
1004	1	1	B

Statistical Analysis Plan**SCR-005: Assessment of the Human Systemic
Absorption of Sunscreen Ingredients**

1005	1	1	D
1006	1	1	B
1007	1	1	A
1008	1	1	C
1009	1	1	C
1010	1	1	B
1011	1	1	A
1012	1	1	D
1013	1	1	B
1014	1	1	A
1015	1	1	D
1016	1	1	C
1017	1	1	B
1018	1	1	A
1019	1	1	C
1020	1	1	D
1021	1	1	A
1022	1	1	D
1023	1	1	C
1024	1	1	B
2001	2	2	G
2002	2	2	E
2003	2	2	F
2004	2	2	H
2005	2	2	E
2006	2	2	G
2007	2	2	F
2008	2	2	H
2009	2	2	G
2010	2	2	E
2011	2	2	H
2012	2	2	F
2013	2	2	F
2014	2	2	G

Statistical Analysis Plan**SCR-005: Assessment of the Human Systemic
Absorption of Sunscreen Ingredients**

2015	2	2	E
2016	2	2	H
2017	2	2	H
2018	2	2	E
2019	2	2	G
2020	2	2	F
2021	2	2	E
2022	2	2	F
2023	2	2	G
2024	2	2	H
2025	2	3	F
2026	2	3	H
2027	2	3	G
2028	2	3	E
2029	2	3	G
2030	2	3	H
2031	2	3	E
2032	2	3	F
2033	2	3	G
2034	2	3	E
2035	2	3	H
2036	2	3	F
2037	2	3	H
2038	2	3	E
2039	2	3	F
2040	2	3	G
2041	2	3	G
2042	2	3	E
2043	2	3	F
2044	2	3	H
2045	2	3	G
2046	2	3	E
2047	2	3	H
2048	2	3	F

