## 5.8.2 Method Assigning Subjects to Treatment

### 5.8.2.1 Randomization Process

### Part 1 and Part 2

The FDA project biostatistician will create the specifications that will be used to generate the randomization schedule. The specifications will be based on the protocol requirements and appropriate statistical programming with consideration for study design, number of treatments, number of subjects planned for enrollment, stratification, and blocking.

Based on these specifications, the project biostatistician (or designee) will generate a dummy randomization schedule. The schedule is generated by a SAS®/R or other program, which produces output file(s) and/or SAS or R dataset(s).

The project biostatistician (or designee) distributes the 'dummy' randomization schedule to specified personnel for review. Any change (e.g., change in block size, change in stratification levels) that requires an update to the specifications will reset this process. Minor changes (e.g., display formatting) will not require a change to the specifications.

No transfer is necessary if the unblinded randomization biostatistician also created the 'dummy' randomization.

The randomization biostatistician is responsible for generating the final randomization schedule.

Randomization will occur after informed consent is obtained, either after completion of check-in procedures on Day 0 or just before dosing on Day 1. Unique subject numbers will be used in sequential order based on each subject's order of qualification.

In both Part 1 and Part 2 of the study, subjects will be randomly assigned to 1 of 4 different treatments, thus each subject will receive one of the sunscreen formulations by the end of the study. For subjects in Part 1: 1) La Roche Posay (Cream), Anthelios SX Daily Moisturizer Cream, Face Sunscreen SPF 15 with Mexoryl SX; 2) Hawaiian Tropic (Lotion); Island Sport Ultra-Light High Performance Sunscreen, SPF 50; 3) Neutrogena (Spray) Ultra Sheer Body Mist SPF 45; or 4) Banana Boat (Spray); Sport Performance Coolzone Continuous Spray Sunscreen, SPF 50. For subjects in Part 2: 1) Hawaiian Tropic (Lotion); Island Sport Ultra-Light High Performance Sunscreen, SPF 50; 2) Neutrogena (Aerosol Spray), Ultra Sheer Body Mist SPF 100; 3) Supergoop (Non-Aerosol Spray), Sunscreen Mist with Vitamin C SPF 50; or 4) Supergoop (Pump Spray), Sun Defying Sunscreen Oil with Meadowfoam SPF 50.

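### SAP Attachment B prints the arm for every randomization number, which the protocol says is locked away, so the next Part 2 assignment is knowable to anyone holding it

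*SAP*

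**What the plan says.** Protocol 5.8.2.1 sets the access rule: "All randomization information will be secured and housed in a locked storage area, accessible only by the randomization personnel and the assigned pharmacist" and that pharmacist's verifier. The same section says how numbers are issued: "Unique subject numbers will be used in sequential order", following the order in which subjects qualify. On timing it says: "Randomization will occur after informed consent is obtained, either after completion of check-in procedures on Day 0 or just before dosing on Day 1". SAP Section 2 places the eligibility decision ahead of the number: "Subjects are considered enrolled after determination by the Principal Investigator on Day 0 that they meet all eligibility criteria", with the number assigned afterwards.

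SAP Attachment B opens with "Randomization in this study is unblinded". It describes the arms and their ingredient percentages, then gives, under the title Treatment schedule, a table of number, part, cohort and arm for 1001 to 1024 and 2001 to 2048. Part 1 is one cohort; Part 2 is two.

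Protocol 5.8.2.1 also distinguishes two lists. It says "the project biostatistician (or designee) will generate a dummy randomization schedule", which is circulated to specified personnel for review; a randomization biostatistician then produces the final one. Attachment B does not say which of the two it prints.

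**The concern.** Open-label treatment removes blinding after assignment. It does not remove the need to conceal an assignment before the decision to admit the subject, and the protocol separately promises that concealment. A list printed in the SAP and used in sequence undoes the promise for whoever holds it.

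Several entry criteria are matters of judgement: whether an abnormal finding is clinically significant, whether skin is irritated, whether venous access is adequate, and whether the subject is highly likely to comply (protocol 5.2.1 and 5.2.2). If the next product is known, those judgements, or the order in which subjects are declared qualified, can depend on it. Part 2 reports four products side by side, and random assignment is what makes those arms comparable.

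**Working it through.** **1. Does the printed list match the design?** Counting the rows of Attachment B:

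- Part 1: 24 rows, with A, B, C and D 6 times each.
- Part 2: 48 rows, with E, F, G and H 12 times each, and 6 times each within cohort 2 and within cohort 3.
- Total: 24 + 48 = 72, the planned enrolment and arm sizes in SAP Section 2.

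So the table is a complete list of the planned size, with one arm per number.

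**2. Can it be used to foresee an assignment?** Set side by side, the investigator decides eligibility on Day 0, the number follows, numbers run in order of qualification, and the arm for each number is printed. A holder who knows how many numbers have been used knows the next arm before the decision.

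**3. How many assignments are at issue?** Attachment B names the lotion carried over from Part 1 as arm E. Protocol 5.1.2 and SAP Section 1.1 say that this choice depends on Part 1 exposure data. This version therefore appears to postdate those data, and it cannot show that 1001 to 1024 were readable in advance. That leaves at most 72 − 24 = 48 assignments, or 24 if cohort 2 had already been assigned when the list was issued.

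**4. What remains if only the table is removed?** Read in fours, Part 2 runs GEFH, EGFH, GEHF, FGEH, HEGF, EFGH in cohort 2 and FHGE, GHEF, GEHF, HEFG, GEFH, GEHF in cohort 3. All 12 sets contain each arm once, as do all 6 sets in Part 1. This is consistent with fixed blocks of four, although neither document states a block size. If the block size were known and each assignment revealed before the next eligibility decision:

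- expected share of correct best guesses = (1/4 + 1/3 + 1/2 + 1)/4 = 0.521, or 25 of 48;
- certain assignments (last in each block) = 12 of 48 = 25%;
- by chance alone, without blocking = 1/4, or 12 of 48.

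If a whole cohort is judged eligible before any number is issued, no earlier assignment in that cohort is visible while eligibility is decided, and these figures do not apply to it.

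**5. Is the order of use clear?** The table has no sex column, yet Part 2 requires 6 men and 6 women per arm. If 24 men and 24 women qualified in random order and the list were used strictly in sequence, the chance of exact balance in every arm would be C(12,6)^4 / C(48,24) = 2.3%. Either some rule not given in the documents governs the order, or the printed list is not the one used.

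**6. How much could it matter?** Each subject carries 1/12 (8.3%) of a Part 2 arm mean. If a subject is replaced by one whose Cmax differs by d, the arm mean moves by d/12.

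**The case against.** The strongest case against is that this is a wording conflict with little practical effect. The study is open-label and exploratory, the primary endpoint is an assayed plasma Cmax, the analysis is descriptive with no between-arm test, and no motive for steering subjects is apparent. Eligibility is already placed before the number, and subjects are studied in cohorts of 24, so a cohort may well be randomized together after check-in. The list may also be only the dummy schedule.

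Much of this stands, and it limits what can be concluded. A reader might infer three stronger things that the documents do not support:

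- That all 72 assignments were known before eligibility was decided. That requires the list to have been with the people judging eligibility, in time. Neither the circulation nor the date of the SAP is given in the text available.
- That the Part 1 comparison that selects the carried-over product was biased. This version appears to postdate that comparison, so it is no evidence on the point.
- That the opening sentence of Attachment B itself shows a failure of concealment. It is consistent with the open-label design; the evidence is the table read with protocol 5.8.2.1.

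What does not stand is the argument that open-label treatment settles the matter, because the protocol restricts access to the list in this same open-label study. Nor does an objective assay protect against selecting who enters each arm. The dummy-list explanation is possible, but nothing labels the table as such, and a dummy too is meant only for specified personnel.

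**Conclusion.** The two documents conflict: protocol 5.8.2.1 restricts all randomization information, and SAP Attachment B prints it. Given sequential numbering by qualification, the next assignment is knowable to anyone holding Attachment B. On this version that concerns at most 48 assignments, all in Part 2.

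The conclusion assumes that the printed list is the operative one, that it is used in sequence, and that it reached someone involved in eligibility before Part 2 enrolment ended. The documents establish none of these three except the sequential rule, and the sex quotas put even that in some doubt. Nothing shows that an assignment was foreseen or steered. The possible effect is a shift in arm-level Cmax summaries, not a false test result, because no between-arm test is planned. The point is still worth correcting, because the change costs almost nothing and makes the concealment promise true.

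**What to change.** - Remove the number-by-arm table from the SAP. Keep the method, the allocation ratio, the cohort structure and the product codes, and hold the list as protocol 5.8.2.1 says. If the printed table is the dummy schedule, say so.
- For each 24-subject cohort, record eligibility and subject order before any number is issued.
- If Part 2 numbers are still unassigned and the printed list is the operative one, regenerate those numbers with a new seed. If all are assigned, record who held Attachment B and when.
- Use undisclosed mixed block sizes only if assignments will be revealed one by one before later eligibility decisions; with whole-cohort eligibility recorded first they are not needed.
- State how the sex balance within arms is reached, since the list carries no sex stratum.

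The cost is one deleted table, a few sentences, and possibly one re-run of the randomization program. It needs no extra subjects or visits.
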